### 11.1.3. Exploratory Endpoints

Additional exploratory analyses may be performed to further investigate study vaccine-elicited immune responses. These may include, but might not be limited to, the following assays:

#### *Humoral immune response*

- Binding antibody levels elicited by vaccination using EBOV GP ELISA at other relevant time points (including Cohort 1 substudy).
- Neutralizing antibody responses against the EBOV GP defined as the serum titer that is able to inhibit viral infection by a certain percentage ( $IC_{50}$ ,  $IC_{80}$  and/or  $IC_{90}$ ) using virus neutralization assay.
- Binding and/or neutralizing antibody responses against the Ad26 and/or MVA vector, using adenovirus and/or MVA ELISA and/or neutralization assays.
- Humoral responses to different EBOV GPs and/or filovirus GPs and/or TAFV NP if assays are available.
- Molecular characterization of study vaccine-elicited antibodies which may include, but will not be limited to: Fc characterization, isotype analysis and epitope mapping.

#### *Cellular immune response*

- The presence and functional capacity of T cells may be determined using pathogen-specific stimulation of PBMC with EBOV GP peptides using IFN- $\gamma$  ELISpot assays. Cytokine-producing T cells can be quantified using ELISpot technology.
- Activation of CD4+ and CD8+ T cell subsets and their cytokine expression patterns may be determined by flow cytometry after EBOV GP-specific stimulation (including, but not limited to, IFN- $\gamma$ , interleukin [IL]-2, and tumor necrosis factor [TNF]- $\alpha$ ) using intracellular cytokine staining (ICS). Exploratory phenotypic and functional analysis may be included.
- Cellular responses to filovirus GPs and/or TAFV NP if assays are available.

### 11.2. Sample Size Determination

An overall planned sample size of 1,056 subjects includes 880 subjects to receive Ad26.ZEBOV and MVA-BN-Filo prime-boost vaccination to substantially contribute to an overall safety data base of the Ad26.ZEBOV and MVA-BN-Filo prime-boost regimen.

In Cohort 1, a total of 550 subjects are planned to be vaccinated with Ad26.ZEBOV and MVA-BN-Filo across the vaccination schedules (220 in Groups 1 and 2, 110 in Group 3). In the other cohorts (2a, 2b, and 3), 55 subjects per vaccination schedule (Groups 1 and 2) are planned to be vaccinated with Ad26.ZEBOV and MVA-BN-Filo, or a total of 110 subjects per subpopulation.

The probability of detecting an adverse event in each of the populations, and total, is given in **Table 9**, for various true incidence rates. In case a specific adverse event is not observed, the one-sided 97.5% upper confidence limit of the true incidence rate of this adverse event is less than 6.5%, 3.3%, 1.7%, 0.8%, 0.7% and 0.5%, for sample sizes of 55, 110, 220, 440, 550 and 880 subjects, respectively.

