**Table 9: Probability of Observing at Least One Adverse Event Given a True Adverse Event Incidence**

True Adverse Event Incidence (%)	N=55	N=110	N=220	N=440	N=550	N=880
0.1	5%	10%	20%	36%	42%	59%
0.5	24%	42%	67%	89%	94%	99%
1.0	42%	67%	89%	99%	100%	100%
2.5	75%	94%	100%	100%	100%	100%
5.0	94%	100%	100%	100%	100%	100%
10.0	100%	100%	100%	100%	100%	100%

Having immunogenicity data available for 55, 110 or 220 subjects per group on Ad26.ZEBOV or MVA-BN-Filo within a cohort, the following pairwise differences in immune response (ELISA antibody levels against EBOV GP) between vaccine schedules can be detected at any given time point, for a given variability in ELISA antibody levels (**Table 10**).

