1.4. Sample Size Justification

An overall planned sample size of approximately 1,056 subjects was to include 880 subjects who were to receive active prime-boost vaccination and 176 subjects who were to receive placebo. The data obtained in these subjects will substantially contribute to the overall safety database of the Ebola program. See Section 11.2 of the CTP¹ for details on the sample size justification.

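### The zero-event upper confidence limit given for 440 subjects (below 0.8%) is not true: the exact limit is 0.835%

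*Protocol*

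**What the plan says.** Section 11.2 of the protocol supports the sample size with two descriptions of safety precision.

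The first is Table 9, "Probability of Observing at Least One Adverse Event Given a True Adverse Event Incidence".

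The second is a sentence on events that do not occur. It begins "In case a specific adverse event is not observed" and goes on to say that the one-sided 97.5% "upper confidence limit of the true incidence rate of this adverse event is less than 6.5%, 3.3%, 1.7%, 0.8%, 0.7% and 0.5" per cent. The six percentages apply "for sample sizes of 55, 110, 220, 440, 550 and 880 subjects, respectively". The n = 440 entry is therefore 0.8%. The Statistical Methods part of the Synopsis repeats the sentence with the same figures. Neither place names the interval method.

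For Cohort 1, the same section plans active vaccination for "220 in Groups 1 and 2, 110 in Group 3". SAP Section 1.4 states no confidence limits and points to protocol Section 11.2 "for details on the sample size justification".

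**The concern.** The sentence makes six inequalities, each of which can be checked from what is printed: confidence level, sidedness, number of events (zero) and sample size are all given. The n = 440 entry looked too small, because the limit falls roughly in proportion to 1/n. Half of the 1.7% stated for 220 subjects would be about 0.85%, which is above 0.8%.

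The primary objective is safety and no hypothesis test is planned, so these limits and Table 9 are what the protocol offers as its safety-precision rationale. If an entry is wrong in the favourable direction, the protocol claims slightly more precision than the design gives. A reader of the SAP is sent back to the same sentence.

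**Working it through.** **Inputs**, all from Section 11.2 and repeated in the Synopsis: one-sided 97.5% confidence, so 0.025 in the upper tail; zero events; n = 55, 110, 220, 440, 550, 880; stated bounds 6.5%, 3.3%, 1.7%, 0.8%, 0.7%, 0.5%.

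**Formula.** The exact (Clopper-Pearson) upper limit with no event solves (1 − p)^n = 0.025, which gives p = 1 − 0.025^(1/n). The 0.975 quantile of a Beta(1, n) distribution gives the same values.

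| n | Exact limit | Stated: less than | True? |
|---|---|---|---|
| 55 | 6.487% | 6.5% | yes |
| 110 | 3.298% | 3.3% | yes |
| 220 | 1.663% | 1.7% | yes |
| 440 | 0.835% | 0.8% | **no** |
| 550 | 0.668% | 0.7% | yes |
| 880 | 0.418% | 0.5% | yes |

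The exact method meets five of the six stated bounds and fails only at 440.

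**Size of the miss at n = 440.**
- Excess: 0.835% − 0.8% = 0.035 percentage points.
- Confidence actually attached to 0.8%: 1 − 0.992^440 = 1 − 0.0292 = 97.08%.
- Subjects needed for a limit below 0.8%: ln(0.025)/ln(0.992) = 459.3, so 460.

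**Could another interval method be behind the list?**

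| Method | n = 55 (stated 6.5%) | n = 440 (stated 0.8%) |
|---|---|---|
| Poisson, −ln(0.025)/n | 6.71% | 0.838% |
| Wilson score | 6.53% | 0.866% |
| Exact, one-sided 95% | 5.30% | 0.679% |
| Rule of three, 3/n | 5.45% | 0.682% |
| Jeffreys | 4.44% | 0.569% |

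The Poisson and Wilson limits exceed the stated bound at both sizes. The last three fall under 0.8% at 440 but are far from 6.5% at 55, and one of them is not at the stated confidence level. Only the exact method fits the other entries closely.

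**Rounding to one decimal.** Rounding the exact limits up gives 6.5, 3.3, 1.7, 0.9, 0.7, 0.5, which differs from the protocol only at 440. Rounding to nearest gives 6.5, 3.3, 1.7, 0.8, 0.7, 0.4, which differs only at 880. Neither rule reproduces the whole list.

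**Does the error reach Table 9?** The N = 440 column is 1 − (1 − p)^440: 35.6% at a true incidence of 0.1%, 89.0% at 0.5%, 98.8% at 1.0%, and 100.0% from 2.5% upwards. The table prints 36%, 89%, 99% and 100%. It is correct.

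**The case against.** The best defence is that this is a rounded value placed after the words 'less than'. To one decimal, 0.835% is 0.8%; five of the six entries equal the exact limit rounded to nearest; and Table 9 also rounds to nearest, printing 100% where the exact value is 99.6% (N = 550, incidence 1.0%). On that view the number is right to its printed precision and only the inequality is loose. This probably explains how the figure arose, but it does not make the sentence true. An upper bound has to be rounded up, and the n = 880 entry was: 0.418% is printed as 0.5%, where nearest rounding would give 0.4%.

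The remaining objections concern weight, and they stand:
- The SAP presents safety by cohort and vaccination schedule, with further tables pooled by vaccine dose. It specifies no safety table that pools only Groups 1 and 2 of Cohort 1, the likely source of 440.
- The sizes are planned numbers. The study pause left some primed subjects without a boost and they are not replaced, so any reported limit will rest on actual counts.
- The pausing rules are event counts, cohort progression rests on review by the data monitoring committee, and no decision rule uses a 0.8% limit.

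**Conclusion.** The concern holds. The statement for n = 440 is false as written in both Section 11.2 and the Synopsis: the exact limit is 0.835%, not below 0.8%. The other five statements are true.

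The conclusion rests on one assumption, that the unnamed method is the exact binomial limit. The list itself supports this, and the Poisson and Wilson alternatives also exceed 0.8% at n = 440. It does not depend on what the 440 represents. That is presumably the active recipients in Cohort 1 Groups 1 and 2 (2 × 220), although the documents do not say so.

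Severity is low. One of six stated precision figures is slightly too favourable. The sample size, the limits for the individual schedules (n = 55, 110, 220), Table 9, the pausing rules and the planned analyses are unaffected.

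**What to change.** In Section 11.2 and in the Statistical Methods part of the Synopsis, replace 0.8% with 0.9% for n = 440 (or with 0.84% if two decimals are preferred). The SAP needs no edit because it only refers to Section 11.2.

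Changing 'less than' to 'approximately' for the whole list would not be enough by itself, because the n = 880 entry would then have to read 0.4% instead of 0.5%.

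The cost is one number in two places, slightly less favourable than before, with no change to sample size, analyses or rules.

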**Table 9: Probability of Observing at Least One Adverse Event Given a True Adverse Event Incidence**

True Adverse Event Incidence (%)	N=55	N=110	N=220	N=440	N=550	N=880
0.1	5%	10%	20%	36%	42%	59%
0.5	24%	42%	67%	89%	94%	99%
1.0	42%	67%	89%	99%	100%	100%
2.5	75%	94%	100%	100%	100%	100%
5.0	94%	100%	100%	100%	100%	100%
10.0	100%	100%	100%	100%	100%	100%

Having immunogenicity data available for 55, 110 or 220 subjects per group on Ad26.ZEBOV or MVA-BN-Filo within a cohort, the following pairwise differences in immune response (ELISA antibody levels against EBOV GP) between vaccine schedules can be detected at any given time point, for a given variability in ELISA antibody levels (**Table 10**).

**Table 10: Magnitude of Pairwise Difference to be Detected Between Vaccine Regimens for a Given Sample Size**

Variability ELISA antibody levels (SD, $\log_{10}$ scale)	Detectable difference, $\log_{10}$ scale *		
	n1=n2=55	n3=110, n1,n2=220	n1=n2=220
0.3	0.19	0.13	0.11
0.4	0.25	0.18	0.14
0.5	0.31	0.22	0.18

SD: standard deviation

\* 90% power, 5% significant level for 2-sided hypothesis, accounting for multiple testing in Cohort 1

### 11.3. Analysis Sets

The Full Analysis set includes all subjects who were randomized and received at least one dose of study vaccine, regardless of the occurrence of protocol deviations. Safety data will be analyzed based on the Full Analysis set.

The Immune Response Analysis set includes all randomized and vaccinated subjects, who have data from baseline and at least one post-vaccination immunogenicity blood draw.

The Per Protocol Analysis set for the main study includes all randomized and vaccinated subjects, who received both the prime and boost (administered not more than 10 days outside the visit window) vaccinations, have immunogenicity data from baseline and at least one post-vaccination evaluable immunogenicity sample, and have no major protocol violations influencing the immune response.

A similar Per Protocol Analysis set will be used for the Cohort 1 substudy for the time points after the third vaccination.

The immunogenicity analysis will be based on the Per Protocol Analysis set. As sensitivity analysis, the immunogenicity data will also be analyzed based on the Immune Response Analysis set, provided more than 10% of subjects in the Immune Response Analysis set are excluded from the Per Protocol Analysis set.

Details on how to handle the data from subjects with a late boost will be described in the SAP, developed before unblinding.

#### **11.4. Subject Information**

For all subjects, demographic characteristics (eg, age, height, weight, BMI, race, and sex) and screening/baseline characteristics (eg, physical examination, medical history) will be tabulated and summarized with descriptive statistics.

#### **11.5. Safety Analyses**

No formal statistical testing of safety data is planned. Safety data will be analyzed descriptively (including 95% confidence intervals, if applicable).

Similar safety summaries will be created for the subjects who received a third vaccination, details will be provided in the SAP.

Baseline for all safety parameters will be defined as the last value before the prime vaccination.

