## COHORT 1 SUBSTUDY TIME AND EVENTS SCHEDULE

### Subjects at Selected Sites Receiving a Third Vaccination (Cohort 1, Groups 1-2)

Groups 1 & 2 b	Vaccination Phase and Post-vaccination Phase					Long-term Follow-up Phase a	
	1 Year Post Prime + 3 months	D2-D7 Post 3 rd Vaccination	D5 Post 3 rd Vaccination	D8 Post 3 rd Vaccination	D22 Post 3 rd Vaccination	D180 Post 3 rd Vaccination	D365 Post 3 rd Vaccination
Study procedures	3rd Vaccination		+4d p3v	+7d p3v	+21d p3v	+6m p3v	+1y p3v
Screening/Administrative							
Informed consent c	X						
Study vaccine administration	▲ d						
Safety assessments							
Urine pregnancy test e	X f						
Physical examination g	X f		X	X	X	X h	X h
Vital signs i	X f						
Distribution of subject diary	X						
Completion of diary at home j		X					
Review of diary by site staff				X			
Adverse events k	Continuous until 28 days after the third vaccination a,l						
Serious adverse events and immediate reportable events m	Continuous a,l						
Concomitant medications	X		X	X	X	X n	X n
Clinical Laboratory Assessments							
Chemistry, hematology (10 mL) o	X f			X			
Immunogenicity Assessments p							
Blood sampling (serum) for assessment of humoral immune responses (10 mL)	X f		X	X	X	X	X
Blood sampling (PBMC) for assessment of cellular immune responses (40 mL) q	X f				X		X
Approximate Blood Volumes with [without] PBMC r							
- By visit (mL) r Cohort 1 (Group 1 and 2)	60 [20]		10	20	50 [10]	10	50 [10]
- Cumulative (mL) r Cohort 1 (Group 1 and 2)	60 [20]		70 [30]	90 [50]	140 [60]	150 [70]	200 [80]

▲ Ad26.ZEBOV 5x10^7 vp or placebo

d p3v: days post third vaccination; m p3v: months post third vaccination; y p3v: year post third vaccination

**NOTE:** In case of early withdrawal from the study, early withdrawal assessments (ie, physical examination and immunogenicity assessments for serum) should be obtained. Subjects who wish to withdraw consent will be offered an optional visit for safety follow-up (before the formal withdrawal of consent); the subject has the right to refuse.

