2. GENERAL ANALYSIS DEFINITIONS

The type I error rate (α) is set to 0.05 and corresponding 2-sided 95% confidence intervals (CIs) will be calculated wherever applicable. Adjustment of the α (type I error) level due to multiplicity is not applicable for this study as no planned formal statistical hypothesis testing will be performed.

The analysis is defined separately for each parameter later in this document together with the description of rules for handling missing or incomplete data. The analysis will include vaccinated subjects with respect to the actual vaccine administered. The subjects who received only Ad26.ZEBOV prime vaccination will be included in accordance with the group to which they were randomization. On the other hand, any subject who was vaccinated according to MVA-BN-Filo prime only, MVA-BN-Filo prime/Ad26.ZEBOV boost or a homologous schedule (ie, Ad26.ZEBOV prime/Ad26.ZEBOV boost or MVA-BN-Filo prime/MVA-BN-Filo boost) will be excluded from summary tables and graphs, and listed separately.

In general, the study data will be analyzed as follows:

- Categorical variables will be summarized with a frequency table presenting counts and percentages.
- Continuous variables will be summarized using the following statistics, as appropriate: number of observations, arithmetic mean, geometric mean, corresponding 95% CI, standard deviation, standard error, median, quartiles (Q1 and Q3), minimum and maximum.

Baseline value will be defined as the value of the last available assessment performed prior to the prime vaccination, unless specified otherwise.

For safety assessments, the *baseline value* will be an assessment performed prior or on the date (if only time of assessment is missing) of the prime vaccination. The baseline value for immunogenicity assessments will be an assessment performed before or on the date of the prime vaccination. In case of multiple values, the value closest to the vaccination will be used as the baseline.

Reference value (only for immunogenicity) will be defined as the assessment performed on the date of the boost vaccination. In case of multiple values (on the same day of vaccination), the value closest to the vaccination will be used as the reference value.

Visit day will be determined relative to the actual day of vaccination (ie, date of Doses 1, 2 or 3).

Repeated assessments of immunogenicity and safety will be allocated to analysis windows and periods based on

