7.2.1. Definitions

In determining toxicity grades, the following rules will be applied:

- Worst grades/abnormalities are determined over the entire period (eg, Post-dose 1, Post-dose 2 or Post-dose 3) separately, including all post-baseline measurements of the corresponding period.
- The abnormalities “abnormally low” and “abnormally high” are considered equally important and both abnormalities are shown in the tables. (This means that the sum of the percentages can exceed 100%).
- If a laboratory value falls within the grading as specified in the grading table but also within the local laboratory normal limits, the value is considered as normal or Grade 0.
- Laboratory results falling between the grading scales will be allocated to the adjacent worst-case grade (because the scale for some parameters in the grading table is not continuous as there may be zones where toxicity grade definitions do not exist).

An abnormality (toxicity grade or abnormality based on normal ranges) will be considered as following vaccination in a period and/or phase if it is worse than the corresponding baseline record. If the baseline value is missing, the abnormality is always considered as following vaccination. A shift from “abnormally low” at baseline to “abnormally high” post-baseline (or vice versa) is also considered as an abnormality following vaccination.

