7.2.3. Analysis Methods

Laboratory abnormalities (except CD4+ cell counts in HIV-infected subjects) will be determined in accordance with the toxicity grading tables (Attachment 3 and Attachment 4), and in accordance with the normal ranges of the clinical laboratory. The worst abnormalities following vaccination will be summarized (ie, showing number and percentage) by regimen and presented per period/phase, with special attention to Grade 3 toxicities. Focus will be on clinical abnormalities that occur during Post-dose 1, Post-dose 2 and Post-dose 3 periods, as well as the Regimen Phase. Similar tables for worst abnormalities will be provided pooled by vaccine (dose). A listing will also be provided for subjects with any abnormal laboratory findings following vaccination. For CD4+ cell counts in HIV-infected subjects, a listing will also be generated.

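### Laboratory abnormalities after the third vaccination are judged against a pre-prime value 12 to 15 months old, although a sample is drawn just before dose 3; the Post-dose 3 tables can both over-count and miss changes.

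*Protocol*

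**What the plan says.** Protocol 11.5 states: "Baseline for all safety parameters will be defined as the last value before the prime vaccination". The same section leaves room for something more specific: "Similar safety summaries will be created for the subjects who received a third vaccination, details will be provided in the SAP".

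SAP Section 2 repeats the rule: "Baseline value will be defined as the value of the last available assessment performed prior to the prime vaccination, unless specified otherwise". It defines one later comparator, and excludes safety from it: "Reference value (only for immunogenicity) will be defined as the assessment performed on the date of the boost vaccination".

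SAP 7.2.1 applies the baseline period by period: "Worst grades/abnormalities are determined over the entire period (eg, Post-dose 1, Post-dose 2 or Post-dose 3) separately". An abnormality "will be considered as following vaccination in a period and/or phase if it is worse than the corresponding baseline record". SAP 7.2.3 makes the result a main output: "Focus will be on clinical abnormalities that occur during Post-dose 1, Post-dose 2 and Post-dose 3 periods, as well as the Regimen Phase".

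In the Cohort 1 Substudy Time and Events Schedule, the row beginning "Chemistry, hematology (10 mL" is marked at two visits: the third-vaccination visit, with a footnote placing the draw before the injection, and Day 8 after it.

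**The concern.** The Post-dose 3 laboratory table should show what changed after dose 3. Under the plan it shows what differs from a value taken before dose 1. The two can disagree in either direction, because a year of ordinary life, the prime and the boost all lie between them.

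Hemoglobin is the most exposed parameter. SAP Attachment 3 grades it only by change: any fall up to 1.5 g/dL is Grade 1, 1.6 to 2.0 is Grade 2, and more than 2.0 is Grade 3. The choice of comparator therefore sets the grade itself. For other parameters it decides only whether a grade is counted.

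The safety and tolerability of a third vaccination is a secondary objective, and these tables support it. The SAP already takes Pre-dose 3 as a comparator for humoral and cellular fold increases (6.2.1.3 and 6.2.2.3), and gives no reason for treating laboratory safety differently.

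**Working it through.** **1. Is there any other safety baseline?** SAP Section 2 allows exceptions to the pre-prime rule, but SAP 7.2 sets none for Post-dose 3. The later reference value is for immunogenicity only. The introduction to the adult laboratory grading table in SAP Attachment 3 speaks of hemoglobin change from a reference, but the table rows say change from baseline, and no pre-dose 3 value is defined for either. The pre-prime value governs.

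**2. Is a pre-dose 3 safety sample really scheduled?** The text of Protocol 9.1.7 does not mention it, so I checked the stated blood volumes of 80 mL, or 200 mL with PBMC.
- Safety samples: 2 × 10 = 20 mL
- Serum samples: 6 × 10 = 60 mL
- Sum: 80 mL, as stated
- PBMC samples: 3 × 40 = 120 mL, giving 200 mL, as stated

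Without the pre-dose 3 safety draw the sums would be 70 and 190 mL. The sample is in the plan.

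**3. How old is the comparator?** Protocol Table 6 puts dose 3 at 12 to 15 months post prime and the next laboratory visit 7 ± 2 days later. At 30.4375 days per month:
- At dose 3: 12 × 30.4375 ≈ 365 days to 15 × 30.4375 ≈ 457 days
- At the Day 8 visit: 365 + 5 = 370 days to 457 + 9 = 466 days
- With the pre-dose 3 sample as comparator: 5 to 9 days

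**4. Which subjects are classified differently?** Illustrative grades at the three samples:

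| Pre-prime | Pre-dose 3 | Day 8 | Counted under the plan | Counted against pre-dose 3 |
|---|---|---|---|---|
| 0 | 0 | 1 | yes | yes |
| 0 | 1 | 1 | yes | no |
| 0 | 1 | 0 | no | no |
| 1 | 0 | 1 | no | yes |

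The second row is over-counting and the fourth is masking. The third shows that persistence matters: the Post-dose 3 period begins at dose 3 administration (SAP Table 2), so the pre-dose 3 sample is outside it, and the only scheduled laboratory sample afterwards is Day 8.

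**5. How many subjects?** The documents give no rate, so this is an assumed range. If the 5:1 ratio carries over to about 90 subjects, active n = 90 × 5/6 = 75 and placebo n = 90 × 1/6 = 15. Let q be the share whose grade worsened after the pre-prime value, was present before dose 3 and persists to Day 8. The expected number miscounted is n × q; the chance of at least one among the active subjects is 1 − (1 − q)^75.

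| q | Active (75) | Placebo (15) | Chance of at least one, active |
|---|---|---|---|
| 1% | 0.75 | 0.15 | 53% |
| 2% | 1.5 | 0.3 | 78% |
| 5% | 3.75 | 0.75 | 98% |
| 10% | 7.5 | 1.5 | >99% |

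With the pre-dose 3 value as reference, these same-grade carry-overs are not counted. The masked cases have no counterpart estimate, because the documents give nothing on how often an entry abnormality resolves and recurs.

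**The case against.** **The phrase in SAP 7.2.1 could mean a period-specific baseline.** The word corresponding allows that reading, but the SAP defines only one safety baseline, so a programmer following it would use the pre-prime value.

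**The substudy endpoints are not laboratory grades.** This stands. Protocol 11.1.2 lists adverse events, SAEs and IREs. Clinically relevant laboratory changes reach those endpoints as investigator-reported events, which SAP Attachment 1 allocates by start date, so an event known to have begun before dose 3 is not assigned to Post-dose 3. A reader might infer that the secondary endpoint is distorted; the documents do not support that.

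**Values within local normal limits are Grade 0.** This also stands and limits the hemoglobin problem. A fall of more than 2.0 g/dL is Grade 3 only if the value also leaves the normal range. Entry selection cuts both ways: Protocol 4.1.1 excludes hemoglobin below the institutional range, so subjects start with room before a fall is graded, but they were chosen as not low, and Protocol 6.2 and 6.3 re-apply no hemoglobin threshold before dose 3.

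**Both arms are treated alike.** True, so in expectation carry-over affects the same share of each arm. With about 15 placebo subjects the contrast is imprecise (1 of 15 has an exact 95% interval of 0.2% to 31.9%). That is a limit of substudy size which a new reference does not remove.

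**Carry-over can be checked.** Partly. The pre-dose 3 draw falls in the Post-dose 2 follow-up phase, and abnormal findings are listed by subject. But SAP Table 2 as written does not close that phase at dose 3, and a listing does not correct the tabulated count.

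**A single pre-treatment baseline shows cumulative change.** It does, which is a reason to keep it as a second display.

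**Conclusion.** The point holds for the descriptive Post-dose 3 laboratory tables. As written, the plan compares Day 8 results with a value 370 to 466 days old when one 5 to 9 days old is available. It can credit dose 3 with changes that preceded it and can hide changes that followed it.

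A reader might infer that the rule simply inflates the Post-dose 3 abnormality rate. The documents do not establish a net direction, because masking also occurs. A reader might also look for a specific excess of severe hemoglobin falls. The documents give no within-subject variability and no share of values that would leave the normal range, so no such rate can be derived.

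The range of about 0.8 to 7.5 miscounted vaccinees rests on two assumptions: that 5:1 carries over to about 90 subjects, and that 1% to 10% have a worsening that persists to Day 8. No formal safety testing is planned, so alpha and power are not affected. The change is worth making because it is cheap and the tables bear on a secondary objective. It does not threaten the study's main conclusions.

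**What to change.** In SAP 7.2.1, for the Post-dose 3 period only:

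- Define the laboratory reference, including the one used for hemoglobin change, as the last value before dose 3 administration. Accept a same-date value only if it was taken before the injection or if only its time is missing, as SAP Section 2 already does for the pre-prime baseline.
- Count an abnormality as following dose 3 only if it is worse than that reference.
- Flag subjects with no sample from the third-vaccination visit and show them against the pre-prime baseline. Do not fall back silently on the 7-day post-boost sample: it is taken about 35 (Group 1) or 63 (Group 2) days after prime, so at dose 3 it would be 365 − 63 = 302 to 457 − 35 = 422 days old, and the stale comparator would return.
- Keep the pre-prime comparison as a secondary display.
- Record the departure from the baseline sentence of Protocol 11.5 in SAP Section 3. Protocol 11.5 already leaves third-vaccination details to the SAP.

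The cost is SAP wording and one derived variable; no new data are needed. The downside is that the report must explain two references.
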